Any subject that has consented and meets inclusion/exclusion criteria will be tested for serum vitamin D levels, and those individuals showing deficiency will be provided supplemental treatment in order to raise vitamin D levels to normal ranges. Individuals who do not show deficiency levels will be included in the study, but will not receive any treatment. These subjects will be added to an additional control group. There will be no payment for enrollment in the study.

b) Inclusion/Exclusion Criteria

Each individual who has given consent will have blood work tested. Should serum vitamin D levels be lower than 30 ng/mL, they will be included in the treatment group. Subjects with normal ranges will be included in the prospective control group. Both male and female athletes will be eligible to enroll. Any individual who currently has a stress fracture or is in the stage of recovering from a lower extremity musculoskeletal injury will be excluded from the study. Questionnaires will be provided in order to gather an understanding of diet, exercise regimen, and related lifestyle questions. Specifically, there will be a question regarding current vitamin D or other multivitamin supplement currently being taken, what the dosage is, and how often it is taken. Female athletes will be provided a separate questionnaire in regards to individual dietary habits and menstrual cycle.

c) Local Number of Subjects

The number of subjects in the study will be based on the number of individuals meeting the inclusion/exclusion criteria and provide written consent. They will be drawn from men's basketball, soccer, and track/field, and women's basketball, soccer, track/field, and cross-country. There will be no cutoff to the number of individuals accepted. Tentatively, there will be roughly 200 athletes enrolled in the study.

d) Study-Wide Number of Subjects

The number of subjects in the prospective portion of the study will be the number of qualified enrollees. This number may change, depending on the length of the study. Should it be necessary to extend the timeline, the study will enroll new subjects for the second season, but will still include them in the test group.

e) Study Timelines

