Analysis of the historic group will follow similar protocol as the recruitment of new subjects. Information from previous subjects will include including gender, age and sports team information. Additional information obtained will include stress fracture occurrence(s) and location, and vitamin D levels (if recorded).

h) Data and Specimen Banking

Data for each enrolled subject will consist of name, age, gender, ethnicity, and sports team. Any personal or private information collected will only be used during data analysis. This may contain information regarding menstruation, dietary habits, and previous pregnancies. Names and private information of subjects will not be released outside of personnel directly attached to the study, and they will not be included in the final study publication. Serum 25(OH) vitamin D levels for each subject will be recorded at the initial examination and 8 weeks following the beginning of treatment. Every injury diagnosis will be recorded per individual. There will be no blood sample banking after vitamin D levels are determined.

i) Statistical Analysis

Sample Size Justification

A power analysis was performed using PASS 2008 software on the research aim to compare the proportion of athletes that experience a stress fracture in those with normal vitamin D levels (either normal at baseline or treated by supplementation) compared to four previous years when this approach was not used. You can see that if the proportion of athletes experiencing stress fracture in the control group is 10%, then if the true reduction in the treated group was to 4% or less, we would have greater than 80% chance (power) in this study to achieve statistical significance in a test of the two proportions.

Two Independent Proportions (Null Case) Power Analysis

Numeric Results of Tests Based on the Difference: P1 - P2

H0: P1-P2=0. H1: P1-P2=D1<>0. Test Statistic: Z test with pooled variance

Power	Sample	Sample	Prop H1	Prop	Diff if H0	Diff if H1	Target Alpha
	Size Grp 1	Size Grp 2	Grp 1 or Trtmnt	Grp 2 or Control			
	N1	N2	P1	P2	D0	D1	
0.9946	200	800	0.0200	0.1000	0.0000	-0.0800	0.0500
0.9509	200	800	0.0300	0.1000	0.0000	-0.0700	0.0500
0.8220	200	800	0.0400	0.1000	0.0000	-0.0600	0.0500
0.6188	200	800	0.0500	0.1000	0.0000	-0.0500	0.0500
0.4048	200	800	0.0600	0.1000	0.0000	-0.0400	0.0500
0.2337	200	800	0.0700	0.1000	0.0000	-0.0300	0.0500
0.1224	200	800	0.0800	0.1000	0.0000	-0.0200	0.0500

Statistical Analyses

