Data collected will include preliminary vitamin D3 serum levels, vitamin D3 serum levels in January, and vitamin D3 levels eight weeks post-supplementation. Additionally, should a stress fracture or other injury occur, the following information will be recorded: name of subject, team, date of injury, activity to cause injury, and location of injury. Each data point will be recorded on a spreadsheet and saved for final analysis. Each individual working on this study will be to date with all required CITI and HIPAA training. Only individuals directly involved with the study will have access to records for the subjects.

k) Confidentiality

Blood samples used for testing vitamin D3 levels will only be kept temporarily. Once each subject has been tested, serum levels will be recorded and samples will be disposed of following laboratory safe handling procedures. The data collected for each subject will be recorded. Any follow-up vitamin D3 tests will follow the same order. Only individuals directly working on the study will have access to the data collected. Personnel collecting blood samples for the vitamin D3 test will temporarily have access to the results for the specific subject being tested.

l) Provisions to Monitor the Data to Ensure the Safety of Subjects

Subjects in this study are only at minimal risk with regards to treatment and testing. Difficulties may arise during administration of vitamin D supplements and during blood sampling.

m) Withdrawal of Subjects

There are several circumstances that may require the subject to be withdrawn from the study without consent. Any subject that ceases activities and involvement with a given sports team will be withdrawn from the study. Likewise, if a subject develops an injury that is not within the parameters of the study will be withdrawn from the study. These injuries may include, but are not limited to, fractures to bones not defined as lower extremity, severe muscles strains that inhibit their ability to perform, ligament sprains or tears that are not directly related to bone strength in the lower extremity, and any other injury that requires the subject to stop sports related activities. Any subject that becomes pregnant during the study will be removed from the study.

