Should it be deemed necessary for a subject to be withdrawn without consent, the subject will be notified and will sign a form acknowledging their release. Any data collected from the subject prior to removal will be kept for partial analysis but will not be included in the final analysis with subjects completing the entire study. Subjects being removed from the study will stop receiving supplemental treatment as part of the study, but may continue if it is beneficial for any injury or health related condition that occurs. Subjects will still be under the supervision of physicians and athletic training staff.

8) Risks to the Subjects

Subjects in the study are being examined for occurrence of stress fractures in the lower extremities. The main purpose of the study is prevention of these injuries, however they are still likely to occur. Stress fractures are the primary injury of note related to this study. Stress fractures show a range of symptoms, from mild discomfort and tenderness to the region, to severe pain and the inability for the subject to function normally. Each injury will be treated individually in order to promote the quickest and safest recovery. Being a sports related study, other injuries and difficulties that may occur outside of the parameters of the study may include torn muscles, tendons, or ligaments, ligament sprains and muscle strains, meniscus tears, bone fractures above the lower extremities, concussions, bruising, dehydration, fainting during training or events, and heat stress. These injuries will be treated by appropriate personnel, but will not be applied towards analysis in the study.

Blood sampling in order to obtain serum 25(OH) vitamin D levels can impact subjects differently. The risks are minimal, but may include slight pain or discomfort, bruising, bleeding, dizziness, becoming light-headed, or fainting. However, blood tests are a normal part of medical treatment and these risks do not put the subject in danger. Supplementation of vitamin D is considered a safe treatment as long as dosages are monitored and adequate. Doses higher than necessary may lead the subject to experience weakness, headaches, dry-mouth, nausea, or other

discomforts. Several possible difficulties may arise from the increased serum calcium levels due to vitamin D. These include heart arrhythmias, kidney problems, and over-active parathyroid function. These problems are very minimal and are unlikely to occur.

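### The power above 80% at 4% versus 10% counts all 200 athletes expected to enrol, while withdrawn athletes are left out of the final analysis and no allowance is made for them

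*Combined protocol and SAP*

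**What the plan says.** **Power.** Section i), Sample Size Justification, gives a PASS table for two independent proportions. The hypotheses are "H0: P1-P2=0. H1: P1-P2=D1<>0" and the method is "Test Statistic: Z test with pooled variance". All seven rows use N1 = 200 and N2 = 800. The row behind the text is "0.8220 200 800 0.0400 0.1000 0.0000 -0.0600 0.0500" (power, N1, N2, P1, P2, D0, D1, alpha). From it the text concludes that, at 4% or less against 10%, "we would have greater than 80% chance (power) in this study to achieve statistical significance in a test of the two proportions".

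**Enrolment.** Section c), Local Number of Subjects: "Tentatively, there will be roughly 200 athletes enrolled in the study". The same section sets no upper limit.

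**Withdrawal.** Section m) has several triggers. One is leaving the team: "Any subject that ceases activities and involvement with a given sports team will be withdrawn from the study". Another is injury outside the study's scope, with a list that ends in "any other injury that requires the subject to stop sports related activities". Pregnancy is a third. Data from withdrawn athletes are "kept for partial analysis but will not be included in the final analysis with subjects completing the entire study".

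**Other injuries.** Section g), Procedures Involved, says that athletes with an injury unrelated to a stress fracture or to the lower extremity stay in the study but go into a separate analysis. Section m) withdraws athletes whose injury falls outside the study's parameters.

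**Historical group.** Section i) refers to four previous years. Specific Aim 1 refers to five. Section g) mentions seasons up to four years back, but gives a chart-review window of January 2010 to August 2015.

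**The concern.** The sample size section and the withdrawal section count different people. The power calculation counts athletes expected to enrol; the final analysis counts athletes who were not withdrawn. The triggers are broad for running, jumping and contact sports followed through a season, and nothing in section i) allows for them.

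This is the only sample size justification in the document, and at 4% it has 2.2 points of slack over 80%. If withdrawals are appreciable, a non-significant Aim 1 result could be read against a power that the stated analysis rules do not deliver. The point concerns the stated power only. Whether excluding withdrawn athletes biases the comparison is a separate question.

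**Working it through.** **Inputs.** From the table in section i): two-sided alpha 0.05, P2 = 0.10, P1 = 0.04, N1 = 200, N2 = 800, pooled-variance Z test. The documents give no removal rate, so losses are varied as an assumption.

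**Formula.** With d = P2 − P1:

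- pooled proportion p̄ = (N1·P1 + N2·P2)/(N1 + N2)
- SE0 = √[p̄(1 − p̄)(1/N1 + 1/N2)]
- SE1 = √[P1(1 − P1)/N1 + P2(1 − P2)/N2]
- power = Φ[(d − 1.96·SE0)/SE1] + Φ[(−d − 1.96·SE0)/SE1]; the second term is negligible at 4%

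**Step 1: reproduce the plan's figure.** N1 = 200, N2 = 800:

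- p̄ = (8 + 80)/1000 = 0.088
- SE0 = 0.02240, SE1 = 0.01745
- (0.06 − 1.96 × 0.02240)/0.01745 = 0.923, and Φ(0.923) = 0.822

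This matches 0.8220. The other six rows also reproduce to four decimals, so the method is identified and the table contains no arithmetic error.

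**Step 2: reduce N1 and hold N2 = 800.** At N1 = 188, p̄ = (7.52 + 80)/988 = 0.08858, SE0 = 0.02303, SE1 = 0.01780, the argument is 0.835 and power is 0.798. The exact column enumerates all binomial outcomes for the same pooled Z rejection rule.

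| N1 analysed | Removed | Power at 4%, plan's formula | Power at 4%, exact | Power at 3%, plan's formula |
|---|---|---|---|---|
| 200 | 0 | 0.822 | 0.831 | 0.951 |
| 189 | 11 (5.5%) | 0.8003 | 0.811 | 0.940 |
| 188 | 12 (6%) | 0.7982 | 0.812 | 0.939 |
| 180 | 20 (10%) | 0.780 | 0.794 | 0.930 |
| 160 | 40 (20%) | 0.729 | 0.747 | 0.898 |
| 150 | 50 (25%) | 0.698 | 0.722 | 0.878 |

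The formula first falls below 0.80 at N1 = 188. Exact enumeration gives 0.801 at 183 and 0.799 at 182, so it first falls below at 18 removed (9%).

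**Step 3: vary N2.** If the historical period is five years of 200 (N2 = 1000, an assumption matching Aim 1), the formula gives 0.814 at N1 = 188, 0.8004 at 182 and 0.798 at 181. The break-even is then 19 removed (9.5%). If the historical group is smaller, the break-even comes sooner: with N2 = 760 it is N1 = 190 (0.798), or 10 removed.

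**The case against.** **Nothing is miscalculated.** This stands. The table is correct for 200 against 800; what is missing is any statement that 200 must be the number analysed.

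**The 6% figure is fragile.** This also stands. At 188 the shortfall from 80% is 0.2 points, exact enumeration moves the break-even to 9%, and a five-year N2 moves it to 9.5%. N2 is not firm in either direction: the documents disagree on four or five years, and section g) applies the inclusion and exclusion criteria to the historical athletes too.

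**The documents have offsets.** Section c) sets no cap and calls 200 tentative. Resources Available and sections d) to f) allow an extension to further seasons with new athletes. These could make up for losses, so 200 is not a ceiling. Neither is linked to a target number analysed, and the power sentence describes 200 against 800 only.

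**The injury rule is unsettled.** Sections g) and m) conflict, so the number removed for other injuries cannot be predicted. Since a separate analysis may also take these athletes out of the main test, the conflict leaves the count uncertain rather than zero.

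**The effect sits at one edge of the claim.** At a true 3%, power is still 0.898 with 160 analysed. But the text claims more than 80% at 4% too, and that is where it can fail.

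A reader might infer that the study is underpowered, or that losses above 5.5% are to be expected. The documents support neither reading: they give no removal rate.

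**Conclusion.** The point holds as a missing allowance for withdrawals. The stated power treats the expected enrolment as the number analysed, and section m) says otherwise. At 4% versus 10%, power falls below 80% after somewhere between 12 removals (6%: plan's formula, N2 = 800) and 18 or 19 (9% by exact enumeration with N2 = 800; 9.5% by the formula with N2 = 1000). A historical group smaller than 800 would bring that forward. At assumed losses of 10% to 25%, power is 0.78 to 0.70 by the plan's formula.

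This rests on the plan's assumed 10% control proportion, on enrolment of 200, and on reading section m) as governing the Aim 1 test. The break-evens are not predictions. The shortfall is small at 6% and grows to 12 points below the stated 0.822 at 25%. The correction is worth making because the claim has little slack and costs almost nothing to restate.

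**What to change.** 1. In section i), state that N1 is the number analysed, and add rows for N1 = 180, 160 and 150 at 4% versus 10% (0.780, 0.729 and 0.698 with N2 = 800).
2. Replace the claim of more than 80% with wording such as: *82% at 4% if all 200 are analysed, falling to about 78%, 73% and 70% if 10%, 20% or 25% are removed (assumed rates)*.
3. Settle whether N2 covers four or five years and use the same period in Specific Aim 1, section g) and section i). If N2 becomes 1000, the four figures are 0.838, 0.796, 0.743 and 0.711.
4. Reconcile sections g) and m) on athletes with other injuries, and say whether they count in the Aim 1 test. Which rule applies is for the sponsor to decide.

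If the sponsor decides to keep removed athletes in the final analysis, N1 = 200 and 0.82 can stand, and section m) should say so.

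The cost is one paragraph, three table rows and consistent wording on the years. No extra enrolment is requested. The stated power becomes somewhat less favourable.

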2. To compare the proportions of 2015-16 academic year student athletes experiencing stress fractures in the vitamin D insufficient or deficient group and the group with vitamin D levels ≥ 30 ng/mL.
3. In 2015-16 athletes, to explore associations between the TRIAD questionnaire risk factors and low baseline vitamin D levels.
4. In 2015-16 athletes, to explore associations between the TRIAD questionnaire risk factors and subsequent stress fractures.

Setting

This study will focus on athletes who are at a higher risk of lower extremity stress fractures. Specifically, this study will be looking at male and female athletes on the track, cross-country, soccer, and basketball teams at the University of South Carolina. During the pre-season physical of each student athlete, serum vitamin D levels will be taken and recorded. There will be a certified nurse to draw the blood samples. This will take place at the University of South Carolina Athletic Department and/or the Palmetto Health Lab at [name]. Potentially, every athlete of the given teams will be enrolled in the study unless they choose not to. Only subjects showing concentrations below 30 ng/mL, which is indicative of insufficient or deficient levels, will be provided supplemental treatment of 25-(OH) vitamin D. Every enrolled subject will be monitored for injury throughout the season. Any and all injuries will be positively identified, and any confirmed stress fractures will be recorded. Data from prospective seasons will be compared to an incidence percentage of athletes from previous seasons. Previous athletes did not receive any vitamin D treatment. These will be used as a control to determine if treatment affected the occurrence of stress fractures. All physicals and tests will be performed at the USC Sports Medicine clinic by the sports medicine staff.

Resources Available

Track, cross-country, soccer, and basketball are all considered high-risk sports due to the constantly high loads being placed on the lower extremities. Basketball is also included because

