of the extreme stresses involved when jumping. Combining all four sports as a single cohort would provide an adequate number of athletes to form a test group. Each sport's season occurs at different times of the year, and indoor sports like basketball and track may have athletes with less sun exposure. This will allow a comparison of occurrences across different sports, not just between treatment and control groups. Depending on the number of individuals meeting criteria for the study, it may be necessary to extend the timeframe to multiple seasons. The initial phase of the study will include a retrospective analysis of data from deficient athletes in these sports from past seasons that have not received any supplemental treatment. This will be used to find the percentage of stress fracture incidences occurring during those seasons.

The staff directly working on the study will consist of a licensed orthopedic surgeon, a doctor of athletic training and nutrition, a physician in occupational medicine, a research assistant, and a master's student. During each individual sport's season, other athletic trainers, physicians, and coaching staff may offer assistance as well. Every individual engaged with the study will be familiar with the basics of the topic and protocol as a minimum. The physicians will provide most of the expertise and insight when providing care for the athletes. Should any unexpected consequences arise, the staff and athletes will have direct access to both orthopedic and athletic training facilities as well as the linked hospital and clinics. The staff is in constant communication and will have regular meetings in order to stay current on the progress of the study.

Prior Approvals

Each individual sports team member, along with the coaching staff, team physicians, and athletic trainers, will be informed of the study. Approval will be required from the teams listed, as well as from the University of South Carolina Orthopedic Clinic.

Study Design

a) Recruitment Methods

Potential subjects will be screened from men's and women's track and field, soccer, and basketball teams, and women's cross-country. Individual players of each described team will be informed of the study during their pre-season physical. It is hoped that every player on the specified teams will be able to enroll in the study, whether they are vitamin D deficient or not.

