1. To compare the proportions of student athletes experiencing stress fractures during the 2015-15 academic year with the four previous years.

A large sample test of the difference in two independent proportions will be carried out, along with computation of 95% confidence interval on the difference between the two proportions. An exploratory logistic regression model will be built with stress fracture as the outcome, group (2015-16 versus the previous four years) as the major predictor variable and type of sport and gender as covariates.

2. To compare the proportions of 2015-16 academic year student athletes experiencing stress fractures in the vitamin D insufficient or deficient group and the group with vitamin D levels ≥ 30 ng/mL.

A large sample test of the difference in two independent proportions will be carried out, along with computation of 95% confidence interval on the difference between the two proportions. An exploratory logistic regression model will be built with stress fracture as the outcome, group (baseline vitamin D deficient versus normal baseline vitamin D level) as the major predictor variable and type of sport and gender as covariates.

3. In 2015-16 athletes, to explore associations between the TRIAD questionnaire risk factors and low baseline vitamin D levels.

Exploratory descriptive and inferential statistics will be carried out, including the building of linear and logistic regression models, looking for an association between the questionnaire items and baseline vitamin D levels (continuous and dichotomized).

4. In 2015-16 athletes, to explore associations between the TRIAD questionnaire risk factors and subsequent stress fractures.

Exploratory descriptive and inferential statistics will be carried out, including the building of logistic regression models, looking for an association between the questionnaire items and the subsequent occurrence of a stress fracture.

j) Data Management

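### Aims 1 and 2 are non-randomised but led by a crude two-proportion test, with the sport- and gender-adjusted model left exploratory; this matters mainly for Aim 2

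*Combined protocol and SAP*

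**What the plan says.** Statistical Analyses, items 1 and 2, have the same structure. First: "A large sample test of the difference in two independent proportions will be carried out", with a 95% confidence interval and no adjustment. Then: "An exploratory logistic regression model will be built with stress fracture as the outcome", with group as the main predictor and "type of sport and gender as covariates".

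The Sample Size Justification powers only the crude comparison for Aim 1: a two-sided pooled-variance Z test, 200 against 800 athletes.

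Neither grouping is randomised. For Aim 1, Setting says: "Data from prospective seasons will be compared to an incidence percentage of athletes from previous seasons". For Aim 2, Inclusion/Exclusion Criteria allocates by serum level: "Should serum vitamin D levels be lower than 30 ng/mL, they will be included in the treatment group".

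Resources Available links sport to the Aim 2 grouping variable, noting that "indoor sports like basketball and track may have athletes with less sun exposure", and plans to compare fracture occurrence across sports. The stratifying variables are available for past athletes too: "Information from previous subjects will include including gender, age and sports team information".

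The plan has no matching, stratification, standardisation or weighting, and no rule for what is concluded if the crude and adjusted results disagree.

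**The concern.** In a non-randomised comparison, a factor related to both the grouping and the outcome biases the crude difference. Sport is such a candidate in Aim 2. The protocol expects it to relate to sun exposure, hence to baseline vitamin D, and thinks it worth comparing fractures by sport. Stability of team composition from year to year gives no protection, because Aim 2 lies within one year.

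In Aim 1 the route is narrower. The 2015-16 athletes must consent, and athletes withdrawn for other injuries or for leaving the team are kept out of the final analysis (Withdrawal of Subjects). Past athletes come from records, and no matching withdrawal rule is stated for them. If consent or withdrawal differs by sport or sex, the two periods differ in mix.

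At stake is a headline difference, with its p-value and interval, that partly reflects who plays which sport, while the result that allows for this carries a label inviting the reader to discount it.

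**Working it through.** **1. The plan's own figure.** Inputs from the Sample Size Justification: n = 200 and 800, rates 4% and 10%, two-sided alpha 0.05.

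- Pooled rate = (200×0.04 + 800×0.10)/1000 = 0.088
- SE under H0 = √[0.088×0.912×(1/200 + 1/800)] = 0.0224
- SE under H1 = √[0.04×0.96/200 + 0.10×0.90/800] = 0.01745
- Power = Φ[(0.06 − 1.96×0.0224)/0.01745] = Φ(0.92) = 0.822

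This matches the stated 0.8220 and confirms that the design rests on the unadjusted two-sided test.

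**2. Aim 2, no vitamin D effect.** The 200 athletes come from Local Number of Subjects. The rest is assumed: 100 athletes in sports with 12% risk, 100 in sports with 4% risk, and deficiency of 60% and 30% respectively.

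| | Higher-risk sports | Lower-risk sports | Expected fractures | Crude rate |
|---|---|---|---|---|
| Low vitamin D (90) | 60 | 30 | 60×0.12 + 30×0.04 = 8.4 | 9.3% |
| Normal (110) | 40 | 70 | 40×0.12 + 70×0.04 = 7.6 | 6.9% |

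The crude difference is +2.4 points with no effect in either stratum. With the deficiency shares swapped, the rates are (30×0.12 + 60×0.04)/90 = 6.7% and (70×0.12 + 40×0.04)/110 = 9.1%, a difference of −2.4 points.

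- Pooled SE = √[0.08×0.92×(1/90 + 1/110)] = 0.0386
- Shift in Z = 0.0242/0.0386 = 0.63
- Rejection rate ≈ P(Z > 1.33) + P(Z < −2.59) = 0.092 + 0.005 ≈ 0.097

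Simulating the example over seven sport-by-sex strata gives about 9% for the crude test. Mantel-Haenszel has a bias of about 0 and rejects about 5% of the time.

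Across a wider assumed range (40 to 100 low athletes, sport risk ratio 2 to 3, higher-risk share 60-70% in the low group against 30-40% in the normal group), mix alone gives 1.3 to 4.5 points and crude false-positive rates of 6% to 17%.

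**3. Price of stratifying in Aim 2.** Effective information is n₁n₀/N.

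- Crude: 90×110/200 = 49.5
- Stratified: 60×40/100 + 30×70/100 = 45
- Ratio: 45/49.5 = 0.91, about 9% less information
- SE ratio: √(49.5/45) = 1.05

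**4. Aim 1, no true effect.** Assumed: past rate 10%, sport risk ratio 3, half of past athletes in higher-risk sports. The stratum risks are then 15% and 5%, and the expected 2015-16 rate is 5% + 10% × (higher-risk share).

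| Higher-risk share, 2015-16 | Expected rate | Crude false positives |
|---|---|---|
| 45% | 9.5% | about 5% |
| 40% | 9.0% | about 6% |
| 30% | 8.0% | about 12% |

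In the 30% row the adjusted logistic model rejects 4.8% of the time. With a balanced mix and a true fall from 10% to 4%, simulated power is 83% crude and 84% stratified.

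**5. Why not simply promote the logistic model in Aim 2.** At 4% to 10% of 200 there are 8 to 20 fractures. With four sport categories (assumed), the model has about five parameters besides the intercept: 8/5 = 1.6 to 20/5 = 4 events per parameter. Mantel-Haenszel copes better with sparse strata.

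**The case against.** The strongest reply is that adjustment is already planned, with exactly these covariates, and that no test is called primary or confirmatory. That is correct. The defect is the status of the adjusted result, not its absence, and the lead role of the crude test is an inference. The inference is reasonable: the crude test comes first, it alone is powered, and the other analysis is labelled exploratory.

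For Aim 1 the reply largely succeeds. A reader might infer that consenting volunteers are set against complete past rosters. The documents do not say so. The retrospective part of Procedures Involved uses the same teams and the same inclusion and exclusion criteria (Resources Available speaks instead of past deficient athletes). Recruitment Methods says "It is hoped that every player on the specified teams will be able to enroll", and 800 past athletes over four years is 200 a year, the number expected in 2015-16. Large shifts in mix have no support in the text, and small ones barely matter.

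A reader might also infer that the headline of either aim could be produced by mix alone. That goes too far. In the Aim 2 example the 95% interval has a half-width of about 7.7 points against a bias of 2.4, and about 90% of such trials would still be non-significant. No scenario tried reached the 6-point difference for which the study is powered. The bias can run in either direction, and the protocol says only that indoor athletes may get less sun.

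What stands is Aim 2: a measured factor that the protocol ties to the exposure is left out of the leading analysis.

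**Conclusion.** The point holds, chiefly for Aim 2. In the worked example the crude difference is off by 2.4 points and the type I error is about 9% instead of 5%. These sizes rest on assumed sport risks and deficiency shares, because the documents give no sport-specific rates; the direction cannot be predicted. For Aim 1 the bias is probably small: about 5% to 6% false positives for a 5- to 10-point shift in mix at an assumed risk ratio of 3. Consent and withdrawals could still move the mix, so the same treatment is sensible for consistency.

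Nor should a stratified Aim 2 result be read as a vitamin D effect. The low group is supplemented, so the contrast mixes low baseline level with treatment, and stratifying cannot separate them. In Aim 1, calendar period, differences in how fractures were ascertained, and athletes who appear in more than one year also remain.

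**What to change.** In Statistical Analyses, item 2, make the Mantel-Haenszel risk difference stratified by sport and sex, with its 95% confidence interval and test, the lead analysis. Do the same in item 1 for consistency. Report the crude difference and its interval as supportive. State in advance that the stratified result governs if the two disagree, and that strata with athletes in only one group carry no weight (n₁n₀/N = 0). If the logistic model is kept for Aim 2, a penalised (Firth) fit would suit the small number of fractures. Add a sentence listing what the adjustment does not address, as set out in the verdict.

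Cost: a change of wording, since sport and gender are already collected in both periods. In the Aim 2 example the standard error rises by about 5% (about 9% less information). In Aim 1 there is essentially no loss of power when the mix is balanced.
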